# 10. STATISTICAL CONSIDERATIONS

## 10.1 Sample Size

A review from June 2015 to May 2019, identified 93 first allogeneic transplant patients with similar conditions, and 66 (71%) of them developed grade 3 or above oral mucositis. With an estimated clinically meaningful effect size of 20% for PBM, the estimated percentage of patients who will receive PBM and develop grade 3 oral mucositis is 51%.

St. Jude Children's Research Hospital  
IRB NUMBER: 19-0225  
IRB APPROVAL DATE: 01/28/2021

We will use the two-stage one-arm design with historical controls to monitor both efficacy and futility. The complete historical control sample will be used in both the interim analysis and final analysis. The test statistic in Chang et al [28] treats the historical control sample as if they are the control arm in a two-arm design. Given the relatively small sample size, we did not use the asymptotic distribution of the test statistic. Instead, we used Monte Carlo methods to estimate the sampling distribution of the test statistic under null and alternative hypotheses by 100,000 Monte Carlo data sets. The simulation program is written in R.

The rules of which accommodate both efficacy and futility. The null hypothesis is  $p_0=0.71$ ; the alternative hypothesis is  $p_1=0.51$ ; The type-I error rate = 0.05 and power 0.8 are used.. The detailed information about the two-stage design is shown in the following table. The attained type-I error rate and power are 0.048 and 0.813, respectively.

Loo k #	n	Boundari es		Boundary Crossing Probability (Incremental)			
				Under H0		Under H1	
		Efficac y	Futilit y	Efficac y	Futilit y	Efficac y	Futilit y
1	40	20	29	0.015	0.508	0.526	0.015
2	66	38	39	0.033	0.444	0.288	0.172
Total				0.048	0.952	0.813	0.187

The expected sample size under null and alternative hypotheses is 56 and 51, respectively. In the historical data between July 2015 and May 2016, 24 patients received allogeneic HCT. We estimate that study accrual of 66 transplant patients will be completed in 31 months after study activation.

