## 10.2 Statistical Analyses

### 10.2.1 Statistical analysis for the primary objective

*To evaluate the feasibility and efficacy of photobiomodulation therapy (PBM) in reducing oral mucositis in children and adolescents at risk for grade 3 oral mucositis undergoing an allogeneic hematopoietic cell transplant (HCT).*

Hypothesis 1: Children and adolescents will receive 75% of the attempted PMB treatment and will be less likely to develop grade 3 oral mucositis from the 1st day of conditioning to day +20 of transplant or engraftment.

Descriptive statistics (counts, percentages, mean, median, standard deviation and interquartile range) and confidence interval will be calculated for the percentage of successful treatment administered, total days on the protocol, days treatment is received, cumulative dose and the number of treatments received at each site.

The count, percentage and confidence interval will be calculated for allogeneic HCT patients who receive PBM and develop Grade 3 mucositis. Whether the percentage of the prospective sample is significantly different from the historical rate is accessed by the monitoring rule in Section 10.1.

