#### 10.2.2 Statistical analysis for the secondary objective

*To compare clinical manifestations associated with the development of oral mucositis between those treated with daily PBM and a matched control. Clinical factors to include: mucositis grade, duration, and days to engraftment.*

*Hypothesis 2: Children and adolescents treated with extra-oral PBM will develop lower grade mucositis, with shorter mucositis duration (days) than the comparison matched control.*

Patients enrolled in the PBM study will be matched to a transplant control that did not receive PBM by age, sex, primary disease and transplant regimen. For a patient receiving PBM, the patients with the same sex, primary disease and transplant regime will be used as the candidate pool. The patient in the pool with the smallest difference of age is selected as matching. If there is more than one patient in the pool that satisfies the smallest difference of age, a reproducible random number generator will be used to randomly select one patient out of the multiple candidates.

The patient identifier, age, sex, primary disease and transplant regime for the patients without PBM in the historical data will be sent to the Biostatisticians without the outcome of development of grade 3 mucositis. The patient identifier for the selected patients in the historical data will be determined. Then other information for these patients will be obtained for analysis.

The two groups will be compared from day 1 of conditioning regimen until engraftment (2 consecutive days of an ANC>500) or Day+20.

The PBM group and the historical group without PBM will be compared on mucositis grade, duration of mucositis (number of days) and days from cell infusion to engraftment. We will compute the descriptive statistics (mean, standard deviation, median, and range) of the duration of mucositis and days to engraftment. We will also compute the descriptive statistics (count and percentage) of mucositis grade. To compare the clinical variables between the PBB and matched control groups, we will use generalized linear model with the variables for matching as covariates. The difference will be assessed by two-sided Wald tests with type I error rate  $< 0.05$ . For the duration of mucositis, the subset of patients who developed Grade 3 mucositis will be compared with their match control patients with similar methods described above.

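### The grade 3 subset test of mucositis duration in Section 10.2.2 selects PBM patients on grade 3 but, read literally, not their matched controls, so it is tilted against PBM

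*Combined protocol and SAP*

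**What the plan says.** Section 10.2.2 pairs each PBM patient with one historical patient of the same sex, primary disease and transplant regimen, taking the nearest age. The historical list "will be sent to the Biostatisticians without the outcome of development of grade 3 mucositis", so controls are chosen blind to grade.

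All PBM patients are then compared with their controls on mucositis grade, duration and days to engraftment. For this, "we will use generalized linear model with the variables for matching as covariates", with two-sided Wald tests at 0.05. The window is stated as follows: "The two groups will be compared from day 1 of conditioning regimen until engraftment" or Day +20.

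A last sentence adds a second duration analysis: "the subset of patients who developed Grade 3 mucositis will be compared with their match control patients with similar methods described above". No section requires those controls to have had grade 3, re-matches them, or adds grade to the model.

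Two other statements bear on the point. Section 10.1 gives the historical rate: "66 (71%) of them developed grade 3 or above oral mucositis". Hypothesis 1, in Section 10.2.1, is that treated patients "will be less likely to develop grade 3 oral mucositis", so grade 3 is an outcome that PBM is meant to change.

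**The concern.** The added test selects one side of each pair on a post-treatment outcome and leaves the other side unselected. The PBM side is entirely grade 3; the control side carries the historical mix. If milder mucositis lasts fewer days, the two sides differ before PBM has done anything.

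The covariates cannot repair this. Sex, disease and regimen are identical within a pair and age is nearly so, which means the matching variables are balanced between the groups. What differs is grade, and grade is not in the model.

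The plan would then yield two p-values for duration. Only the all-patient one answers Hypothesis 2. The other leans towards longer duration with PBM, and no rule says which prevails if they disagree.

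**Working it through.** The plan states no operating figure for this test, so there is none to reproduce. The check takes the plan's grade 3 rate and works out the bias.

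**Inputs from the documents**
- Historical grade 3 or above: 66/93 = 0.71 (Section 10.1). PBM rate under the design alternative: 0.51 (Section 10.1).
- Sample: 66 pairs, or a stop at 40 if 20 or fewer, or 29 or more, of the first 40 PBM patients have grade 3. Treating the boundaries as fixed counts, the stop probability is 0.50 under no effect and 0.52 at 51%. The table in Section 10.1 adds to 0.015 + 0.508 = 0.523 and 0.526 + 0.015 = 0.541, which is close.
- Durations (Section 2.2, HCT Patient Experience at St. Jude): medians of 11 days of mucositis, 9 days from onset to engraftment, and 2 days from engraftment to the end of mucositis.

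**Assumptions**
- Grade 3 episodes average 9 days. The comparison window closes at engraftment or Day +20, so the onset-to-engraftment figure fits it best; 11 days is a sensitivity case.
- Milder cases average 4, 6 or 8 days. Durations are gamma with coefficient of variation (CV) 0.5.
- Within-pair correlation of grade (latent normal) is 0, 0.25 or 0.5.

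**Step 1: size of the bias.** Under no effect,

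bias = P(control below grade 3 | PBM partner has grade 3) × (mean grade 3 duration − mean milder duration).

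The first factor is 29.0%, 24.7% and 19.9% at correlations 0, 0.25 and 0.5. For example, 0.29 × (9 − 4) = 1.45 days and 0.199 × (9 − 6) = 0.60 days.

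**Step 2: how often the test goes wrong.** Simulation under no effect, two-sided 5% test, 100,000 runs per cell. The average subset is 0.71 × 66 = 47 pairs, or 38 allowing for the stop. Nominal is 2.5%.

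| Grade 3 / milder (days) | Correlation | Mean difference (days) | PBM significantly longer, 66 pairs | With stop |
|---|---|---|---|---|
| 9 / 4 | 0 | +1.45 | 35.0% | 29.6% |
| 9 / 6 | 0 | +0.87 | 16.4% | 14.2% |
| 9 / 8 | 0 | +0.29 | 5.2% | 4.9% |
| 9 / 4 | 0.25 | +1.24 | 27.0% | 23.0% |
| 9 / 6 | 0.25 | +0.74 | 13.0% | 11.3% |
| 9 / 8 | 0.25 | +0.24 | 4.6% | 4.4% |
| 9 / 4 | 0.5 | +0.99 | 19.1% | 16.6% |
| 9 / 6 | 0.5 | +0.60 | 9.9% | 8.9% |
| 9 / 8 | 0.5 | +0.20 | 4.3% | 4.1% |
| 11 / 4 | 0 | +2.03 | 42.7% | 35.8% |
| 11 / 8 | 0.5 | +0.59 | 8.0% | 7.2% |

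With the 9-day input and the stop, the range is 4.7% to 46.5% at CV 0.35 and 3.6% to 18.5% at CV 0.7.

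**Step 3: does adjustment help?** In a linear model with a covariate that takes the same value in both members of a pair, the group indicator is uncorrelated with the covariate, so the adjusted difference equals the raw one. In simulation the rejection shares moved by at most 0.4 points. A gamma log-link model with group only moved them by at most 1.4 points.

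**Step 4: comparators under no effect.** Grade 3 against grade 3 gives 0.0 days and 2.4% to 3.0% per tail. The all-patient comparison is also centred on 0.0 days.

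**Step 5: if PBM works.**
- PBM only lowers grade 3 from 71% to 51%, 9-day input, 66 pairs. The all-patient difference is −(0.71 − 0.51) × gap: −0.20 days at a 1-day gap and −1.00 at a 5-day gap. The literal subset test shows +0.15 to +1.44 days, the opposite sign.
- PBM also shortens every episode by 20%. Power to show shortening, over all inputs:

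| | All patients | Grade 3 vs grade 3 | Literal test |
|---|---|---|---|
| 66 pairs | 80% to 93% | about 52% | 3% to 39% |
| With stop | 69% to 86% | about 43% | 3% to 32% |

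The drop from the first column to the second reflects a smaller subset and a different question. Only the drop from the second to the third is bias.

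**The case against.** **The sentence may mean grade 3 in both groups.** It does not name a group, and on that reading the null bias is zero. But it speaks of these patients' own matched controls, which points to the paired, unselected ones. Two analysts could run different tests. The looser reading also still conditions on an outcome that PBM is meant to alter.

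**The size is assumed.** This stands. The documents give neither duration by grade nor a standard deviation, and the 9-day and 11-day figures come from the same account, neither clearly tied to grade 3 patients. Nine days is also a median time to engraftment used here as a mean duration. Because the window closes at engraftment, it may compress the gap between grades, so 9 against 4 days is best read as an upper case for that input. The simulation also assumes distinct controls, which the plan does not promise. Only the direction is firm, and only if milder mucositis is shorter and matching does not fully determine grade.

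**Matching may predict grade better than a correlation of 0.5.** This is possible, since pairs share the regimen. At correlation 0.8, about 12% of controls are below grade 3, the bias is 0.1 to 0.6 days, and PBM is falsely longer in about 4% to 10% of trials. At 0.95 the figure is about 3% to 6%. The bias shrinks but does not reverse.

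**The consequence is limited.** This also stands. It is one supplementary sentence under a secondary objective, and the error runs against PBM.

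**Conclusion.** The concern holds. As written, the subset test compares PBM patients selected for grade 3 with controls not so selected, and it leans against PBM whenever milder mucositis is shorter and matching leaves some controls below grade 3.

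The middle case (9 against 6 days, correlation 0.5) gives +0.6 days and a 10% chance of a falsely significant lengthening, or 9% with the stop. All sizes are illustrative. The test cannot support a false claim of benefit, but it can mask a real shortening or contradict the valid all-patient result. It should be fixed before analysis.

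**What to change.** Delete the last sentence of Section 10.2.2, or replace it with wording such as: *Duration among patients who developed grade 3 or above mucositis will be described in each group without a test.* Base inference on duration on the all-patient comparison already in that section.

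Stating only that controls must also have grade 3 would remove the null bias, but the test would still condition on an outcome PBM is meant to change. The descriptive version shares that limit, which is why it should carry no p-value; deletion avoids it altogether.

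The cost is one sentence and one supplementary p-value. No new patients, data or chart abstraction are needed.

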#### 10.2.3 Statistical analysis for the exploratory objective

**To evaluate efficacy of photobimodulation therapy in autologous patients at risk for  $\geq$  grade 3 oral mucositis compared to matched control.**

The count, percentage of developing Grade 3 mucositis and its confidence interval will be calculated for autologous HCT patients who receive PBM. In the historical data between July 2015 and May 2016, 8 neuroblastoma patients who received autologous HCT were at risk for grade 3 mucositis. It is expected that – 22 autologous HCT patients will be treated with PBM. Fisher's exact test or two-sided Wilcoxon rank-sum test with type I error rate  $< 0.05$  is used to compare these patients with the patients in the historical data. The matching is based on age, sex, primary disease, and conditioning regimen.

**To evaluate utilization of play-based procedural preparation and treatment feasibility and parental satisfaction.**

Descriptive statistics (counts, percentages, mean, median, standard deviation and interquartile range) and confidence interval will be calculated for the percentage of successful treatment administered, total days on the protocol, days treatment is received, cumulative dose and the number of treatments received at each site between those who had procedural based preparation and those that did not. Descriptive statistics (counts, percentages, mean, median,) will describe parental satisfaction.

## 10.4 Anticipated Completion Dates

Anticipated Primary Completion Date : 35 months after activation
Anticipated Study Analysis Completion Date: 1 year after completion
Anticipated date of reporting: 2 years after completion

## 11. OBTAINING INFORMED CONSENT

The process of informed consent will follow institutional policy. Informed consent should be obtained by the principal investigator, [name], RN, [name], [name], CRA or [name] CRA, in the presence of at least one non-physician witness. Eligible parents will first be approached by a member of the study team regarding the study purpose, methods and design details. Only with parental permission will the eligible patients be approached regarding participating in the study. Both verbal and written assent and consent procedures will be completed in a private room and following our institutional guidelines. The consent/assent process will be documented in the medical record per institutional guidelines. Patients and parents may decline participation without any negative repercussions whatsoever. Refusals will be documented in the research records and examined for any possible patterns. All patients who meet eligibility criteria regardless of gender or minority status are fully eligible to participate in this study. Any adverse effects experienced by participating patients during their enrollment on this protocol will be reported to the IRB at both sites within 48 hours. At the time of consent, documentation will be made in the medical record specific to patient and parental information regarding COVID-19 risk and distribution of COVID information sheet.

### 11.1 Consent at Age of Majority

The age of majority in the state of Tennessee is 18 years old. Research participants will be reconsented should they become 18 during the study period. must be consented at the next clinic visit after their 18th birthday.

### 11.2 Consent When English is Not the Primary Language

When English is not the patient, parent, or legally authorized representative's primary language, the Social Work department will determine the need for an interpreter. This information documented in the participant's medical record. Either a certified interpreter or the telephone interpreter's service will be used to translate the consent information. The process for obtaining an interpreter and for the appropriate use of an interpreter is outlined on the Interpreter Services, OHSP, and CPDMO websites.

